Intervention method	When the transfusion departments of the participating hospitals encounter the patients with the rare primary RhD negative blood group who needed to apply for blood transfusion in non-emergency situations, the application form and blood samples of the patients were sent to the reference lab of Guangzhou Blood Center for "Asia type" DEL blood group typing. The patients identified as "Asia type" DEL blood group and meeting the inclusion criteria will be provided the compatible RhD+ blood with the same ABO type after cross-matching test by Guangzhou Blood Center. RhD+ blood transfusion for the patients with "Asia type" DEL blood group was performed in the cooperated hospitals in line with the Technical Specifications for Clinical Blood Transfusion .
Evaluation index for effectiveness	Hemoglobin concentration (Hb); Hematocrit (Hct) etc.
Evaluation index for safety	
1. Incidence of anti-D alloimmunization;
 
2. Incidence of adverse blood transfusion reactions;
 
3. Observation of vital signs: temperature, heart rate, breathing, blood pressure etc.;
 
4. Laboratory testing;
 
5. Incidence and severity of other adverse events.

Visiting time	
Phase I of Visiting: -7~ 0 days before transfusion;
 
Phase II of Visiting: Blood transfusion treatment period (0~1 days) ;
 
Phase III of Visiting: 1 day to 1 month after blood transfusion;
 
Phase IV of Visiting: 1 month to 12 months after blood transfusion (based on the actual return visit in the hospital or follow-up at home) ;
 
Phase V of Visiting: Over 12 months after blood transfusion.

Statistical Analysis	As the "Asia type" DEL is a rare blood group with a frequency of around 0.75-1‰ in East and Southeast Asian population, it is not feasible to collect the enough samples to conduct the common statistical analysis. So, the descriptive statistics was regarded as the principal analysis method in this study. Continuous variables are described by number of cases, mean, standard deviation, median, minimum, and maximum; categorical variables are summarized by frequency and percentage. Statistical analysis is conducted using SAS9.4 statistical software.
Number of research centers	A total of 9 hospitals participate the trial.
Progress of the trial	The trial is expected to be completed within 48 months after beginning.

Protocol · Text

I. Research Background

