When filling out the adverse event form, the researchers will use "mild, moderate, and severe" to describe the extent of the adverse event. To harmonize the standards, the levels of incidents are classified as follows:

- ✧ Level 1: Mild, short-term (less than 48 hours) or minor discomfort, no need for treatment;
- ✧ Level 2: Moderate, Mild or moderately restricted movement, may require medical attention, no or only need for minor treatment;
- ✧ Level 3: Severe, movement is significantly limited, requiring medical attention and treatment, and may require hospitalization;
- ✧ Level 4: Severe or potential life threatening, severely restricted movement, requiring treatment, emergency or hospitalization.

The grading of the clinical observation indicators (local manifestation, vital signs, and systemic manifestation), laboratory testing indicators (blood biochemistry, blood routine, and urine routine), the clinical abnormalities, and the adverse events in the trial can refer to *the Guideline of the Grading Standard for the Adverse Events in Preventive Vaccine Clinical Trials*.

(III) Evaluation of the correlation between adverse events and research interventions

The researcher should conduct a comprehensive analysis according to the specific circumstance of adverse events of the subject and the subject's previous medical history, concomitant disease, and concomitant medication, to determine the relationship between the adverse event and the drug (product or treatment) with reference to *the Manual of Adverse Drug Reaction Reporting and Monitoring* issued by the State Drug Administration in November 2012 and *the Administrative Measures for Adverse Drug Reaction Reporting and Monitoring* implemented on July 01, 2011 (Order of the Ministry of Health No. 81). As far as possible, it should try to determine the relationship between the adverse events (including serious adverse events) and the drug (product or treatment). If it is determined to be related, no matter the conclusion is to be positively related, likely to be related, or may be related, all these will be regarded as adverse reactions caused by the intervention, and the incidence of adverse reactions will be counted.

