The five principles for evaluating the correlation between the intervention methods and adverse reactions: First, is there a reasonable time relationship between the intervention methods and the occurrence of adverse reactions/events? Second, does the response conform to the type of adverse reactions known to the intervention method? Third, does the reaction disappear or alleviate after the intervention method is stopped? Four, does the same reaction/event occur again when the method is used again? Five, can the adverse reaction/event be explained by the effect of

the combined medication/treatment, the progress of the patient's condition, and the impact of other treatments?

According to the above five principles, the relevance evaluation is classified into 6 levels of positive, very likely, possible, possibly irrelevant, to be evaluated, and unable to be evaluated.

Principles Results	①	②	③	④	⑤
Positive	+	+	+	+	—
Very likely	+	+	+	?	—
Possible	+	±	±?	?	±?
Possibly irrelevant	—	—	±?	?	±?
To be evaluated	With a need to supplement evidence to evaluate				
Unable to be evaluated	The necessary materials for evaluation are not available				

Note: '+' means positive; '—' means negative; '±' means difficult to affirm or negative; '?' means unknown

(IV) Adverse events management

Any adverse event, such as discomfort and abnormal laboratory tests of the subject, should be treated seriously, analyzed carefully, and immediate measures should be taken to protect the safety of the subjects.

1. Handling procedure

The adverse events occurred during the trial should be recorded in the CRF forms in terms of type, degree, occurrence time, duration, treatment measures, treatment process and outcome, etc. And to evaluate the relevance of the trial interventions with the reverse events based on the comprehensive consideration of comorbidities and combined medications and then recorded in detail by the physician. The investigator should follow up the adverse event until the symptoms disappear or stabilize. For the more serious adverse events, it should be followed up for a longer period, and the follow-up ways can be inpatient, outpatient, telephone, etc. The adverse events happened at the end of the study need to be followed up within one month after the study end. It should follow up the cases withdrawn due to adverse events and adverse reactions, and to record the continuity, outcome, and disappearance in detail.

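### Under the counting rule in IX(III), events with pending or unassessable causality drop out of the adverse-reaction incidence, which could understate it

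*Combined protocol and SAP*

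**What the plan says.** Section IX(III) contains the only sentence that says which adverse events enter the reaction incidence. Its condition is that the event has been determined to be related, "no matter the conclusion is to be positively related, likely to be related, or may be related", and its consequence is that "all these will be regarded as adverse reactions caused by the intervention, and the incidence of adverse reactions will be counted".

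The same section then sets out the scale: "the relevance evaluation is classified into 6 levels of positive, very likely, possible, possibly irrelevant, to be evaluated, and unable to be evaluated". The relevance table explains the last two levels. *To be evaluated* means "With a need to supplement evidence to evaluate". *Unable to be evaluated* means "The necessary materials for evaluation are not available".

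The Protocol Abstract lists "Incidence of adverse blood transfusion reactions" as the second safety index, after anti-D alloimmunization. Sections VI(III) and VIII(II) have transfusion reactions observed and recorded while the transfusion is given, and mention no causality level.

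Section XII(II)2 analyses safety in subjects with at least one transfusion. It summarises AE, TEAE, SAE and AESI with no stated causality filter. It also lists, with relationship to the intervention, subjects who stopped treatment because of an adverse event, had an SAE or died. It does not define the reaction incidence by causality level and does not mention the two unresolved levels.

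**The concern.** A pending or unassessable rating is missing information. The literal rule gives such an event the same weight in the reaction count as one rated *possibly irrelevant*, namely none. This sits oddly with the rest of the rule, which is cautious about uncertainty: an event that may be related is counted as a reaction. An event about which still less is known is not.

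The practical consequence is that poorer documentation can only lower the reported reaction rate. The trial is single-arm, descriptive and without a fixed sample size, so a reader will take the raw percentage at face value.

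Unassessable events are plausible, though their number is unknown. Section VII(II) lists liver, renal and electrolyte values before and after transfusion, but neither section VIII nor the flow chart schedules a routine liver or renal test after the first stage. According to the Protocol Abstract, the visit between 1 and 12 months depends on actual return visits or follow-up at home.

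**Working it through.** There is no figure in the plan to reproduce. It states no sample size, no expected reaction rate and no expected number of unresolved events. The check is first a comparison of the rule with the scale, and then a bound.

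**Step 1. Rule against scale (both in IX(III)).**

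| Level in the scale | Nearest term in the counting rule | Counted under the literal rule? |
|---|---|---|
| Positive | positively related | yes |
| Very likely | likely | yes |
| Possible | may be related | yes |
| Possibly irrelevant | none | no |
| To be evaluated | none | no |
| Unable to be evaluated | none | no |

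Three of six levels are counted. Of the three that are not, one is a judgement against a relation and two are the absence of a judgement. The labels of the second and third rows also differ between rule and scale, so the match is by sense only.

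**Step 2. Bound on the effect.** Let n be the safety set (XII(I)), x the subjects with at least one event counted under the rule, and u the further subjects whose only candidate event is unresolved.

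- Present rule: x/n.
- All unresolved events counted as related: (x + u)/n.
- Largest possible shortfall: (x + u)/n − x/n = u/n.

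Given how the rule treats assessed events, the incidence that full causality information would give lies between these two values. The omission can therefore move the result in one direction only, downward.

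**Step 3. Illustration.** All values of n, x and u are assumptions.

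| n | x | u = 0 | u = 1 | u = 2 | Shortfall for u = 1 to 2 |
|---|---|---|---|---|---|
| 20 | 1 | 1/20 = 5% | 2/20 = 10% | 3/20 = 15% | 5 to 10 points |
| 50 | 2 | 2/50 = 4% | 3/50 = 6% | 4/50 = 8% | 2 to 4 points |
| 100 | 5 | 5/100 = 5% | 6/100 = 6% | 7/100 = 7% | 1 to 2 points |

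For scale, the exact (Clopper-Pearson) 95% interval is 0.1% to 24.9% for 1/20 and 1.6% to 11.3% for 5/100. In these cases the shift lies within sampling uncertainty, but unlike sampling error it always has the same sign.

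**Step 4. What is not touched.** Anti-D alloimmunization is detected by antibody screening (section VIII) and does not pass through this scale. The AE, TEAE, SAE and AESI summaries carry no stated causality filter, so unresolved events remain in them.

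**The case against.** The strongest reply has five parts.

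- **Exclusion is not stated.** A reader might infer that the plan expressly excludes unresolved events, or treats missing information as proof of no relation. The documents do not support that. No sentence excludes them, and the scale keeps them apart from *possibly irrelevant*. What stands is that an event with no causality judgement has not been determined to be related, so the counting condition is not met.
- **Bias is not shown.** A reader might also infer that the safety result is biased downward. That requires unresolved events to remain at analysis and some of them to be truly related; neither can be known from the plan. The rule also counts merely possible events, which may raise the incidence, so the net direction of all classification error is not established. Counting possible events is, however, a separate choice and does not repair the gap for unresolved ones.
- **The endpoint link is not explicit.** The listed index is adverse transfusion reactions, which are also recorded directly during transfusion, whereas IX(III) speaks of adverse reactions in general. This objection stands: the plan does not say whether the index is derived from the scale. Home follow-up bears only on later events, and telephone contact is mentioned for following up events already found.
- **Other provisions help.** IX(III) asks for causality to be determined as far as possible, IX(IV) requires abnormal safety tests to be repeated and analysed, and XI(II) locks the data only once queries are settled. These may clear many pending ratings. They cannot supply materials that do not exist, and none names the two levels.
- **Events stay visible.** This is true of the all-cause summaries. The individual listing with relationship, however, covers only SAEs, deaths and events that ended treatment, so a non-serious unassessable event need not appear in it. Nor do the summaries correct the reaction rate.

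The stated purpose is to explore safety and effectiveness, so the point should not be argued as if the trial set out to demonstrate safety.

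**Conclusion.** The point holds in limited form. Read literally, the rule in IX(III) handles events rated *to be evaluated* or *unable to be evaluated* in the same way as unrelated events when the adverse-reaction incidence is counted, and section XII does not provide otherwise. If such events remain at analysis and some are truly related, the incidence is understated by at most u/n. The actual size cannot be computed because the documents give neither u nor n. It is zero if no subject depends on an unresolved event, and a few points in a small safety set if one or two do.

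The conclusion rests on reading the counting condition as written and on a per-subject incidence in the safety set. It reaches the transfusion-reaction index only if that index is derived from this scale, which the plan leaves open. This is a cheap improvement to the reporting of one safety measure and does not put the trial's main safety finding in doubt.

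**What to change.** In IX(III) and XII(II)2:

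1. Require every *to be evaluated* rating to be resolved before database lock, moving to *unable to be evaluated* only when the materials cannot be obtained.
2. Report the reaction incidence twice: by the present rule, and with any remaining *to be evaluated* or *unable to be evaluated* events counted as related.
3. Give the number of such events and of the subjects concerned, and list the events individually.
4. State whether the adverse transfusion reaction index is derived from this scale, from direct observation during transfusion, or from both.
5. Use one set of labels in the counting rule and in the six-level scale.

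The cost is a few sentences, one extra table row and a short listing. The second figure may be slightly less favourable than the first. Showing both is enough; the plan need not adopt the higher one as its headline.

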patients receive D+ blood transfusion, and D+ blood transfusion is only allowed in the condition of emergency or lacking of D- blood supply for "Asia type" DEL patients [18]. In summary, this clinical study has important practical significance and can provide basic evidence whether anti-D alloimmunization will occur in "Asia type" DEL patients with ordinary D+ blood transfusion. If a new strategy of D+ blood transfusion in "Asia type" DEL patients can be established in the future, that is, the routine "Asia type" DEL testing in patients with a primary D- phenotype could be performed, and then to treat the "Asia type" DEL patients as ordinary D+ patients, rather than the rare D- patients in clinic. It will save at least 25% of rare D- blood in East and Southeast Asian countries, and it will also prevent "Asia type" DEL pregnant women receive anti-D immunoglobulin injection and other medical intervention/monitoring to prevent anti-D associated fetal neonatal hemolytic disease, which also could save the precious blood product anti-D immunoglobulin that derived from the sera from the D- volunteers who are sensitized.

II. Purpose of the trial

To explore the safety and effectiveness of RhD+ blood transfusion in Chinese "Asia type" DEL patients to lay the foundation for establishing a new blood transfusion strategy for "Asia type" DEL patients.

III. Design of the trial

The aim of this study is to analyze whether anti-D alloimmunization will occur in "Asia type" DEL patients after D+ blood transfusion, and then to compare the results with the data from the true D- patients received D+ blood transfusion to determine the "Asia type" DEL patients should be treated as D+ or D- patients in the future. The ideal study control group is the incidence of anti-D alloimmunization of true D- patients receiving D+ blood transfusion. But for ethical reasons (according to the requirements of *Technical Specifications for Clinical Blood Transfusion*, true D- patients can only be transfused with D+ blood in urgent situation or lacking of D- blood supply), and it is not appropriate to set up the control group (to transfuse D+ blood in true D- patients in non-emergency situations). Although the summarized rate of alloanti-D occurrence (22.9%, 53/231) [19-22] in true D- patients transfused with D+ blood in previous reported studies could be used as the control for the statistical analysis including sample size calculation, our study could not satisfy

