the demands as the “Asia type” DEL transfusion satisfied the inclusion criteria belong to a rare event because of the rare distribution of “Asia type” DEL in our population (0.75-1‰). In theory, more than 2000 “Asia type” cases receiving D+ blood transfusion, which covering around fifty millions population, are necessary to compare the difference of alloanti-D occurrence between the “Asia type” DEL patients group in our study and the true D- control patients group with similar disease categories receiving D+ RBCs transfusion. It is not feasible in practice for this study.

Therefore, a multi-center, single-arm clinical trial was performed in this study. When any hospital in Guangzhou city applies for D- blood supply in a non-emergency situation, routine “Asia type” DEL typing, antibody screening and identification, and cross-matching test for “Asia type” DEL patients were conducted in the reference lab of Guangzhou Blood Center. The “Asia type” DEL patients meeting the inclusion criteria were recruited in each cooperative hospital. After the informed consent for D+ blood transfusion was obtained from the patient or family members, cross-matched D+ blood was provided by Guangzhou Blood Center. D+ blood transfusion was performed at the corresponding hospital according to *Technical Specifications for Clinical Blood Transfusion* [23] and *Technical Guidelines for Vaccine Clinical Trials* [24].

IV. Selection of Subjects

(I) Inclusion criteria (same to the Protocol Abstract)

(II) Exclusion criteria (same to the Protocol Abstract)

(III) Rejection criteria

1. Cases that did not meet the inclusion criteria or belong to one of the exclusion criteria after enrollment;
2. Cases who did not receive blood transfusion finally in clinic after enrollment.

(IV) Dropout criteria

1. All patients, who signed the informed consent of blood transfusion, meet the inclusion criteria and enrolled, but failed to complete the follow-up observation in accordance with the protocol requirements;
2. The subject requested to withdraw from the trial;

3. In the trial, if the subject has an adverse event that prevents him/her from completing the clinical trial, the investigator should record the process and outcome of the adverse event in detail, and make a judgment on the cause and effect of the trial. Cases dropout due to adverse events should be included in the statistical analysis of adverse events, but were not included in the evaluation of efficacy;

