 - 5) Liver function testing: alanine aminotransferase (ALT), aspartate aminotransferase (AST), total bilirubin (TBIL), direct bilirubin (DBIL), total plasma protein (TP), plasma albumin (ALB);
 - 6) Renal function testing: Urea, creatinine (Cr);
 - 7) Examination of coagulation function: prothrombin time (PT), activated partial thromboplastin time (APTT), thrombin time (TT), fibrinogen (FIB);
 - 8) Urine routine;
 - 9) Stool routine, occult blood test;
 - 10) Pregnancy test: The women patients who reach menopause, or are undergoing menstruation at the time of the test, or have undergone birth control surgery do not need to have a pregnancy test, but need to record the reason for not doing so.
 - 11) Electrocardiogram.
4. Combined treatment/medication;
5. Evaluation of the patients for participation of this study based on inclusion and exclusion

criteria.

(II) Phase II of Visiting: Blood transfusion treatment period (0~1 days)

1. To record the detail of transfusion, including the time of transfusion start and end, the type of transfusion, the volume of transfusion, and to observe the adverse reaction during the transfusion treatment;
2. Observation of vital signs: temperature, heart rate, breathing, blood pressure;
3. Observation and recording of adverse events;
4. Combined treatment/medication.

(III) Phase III of Visiting: 1 day to 1 month after blood transfusion

1. Physical examination, observation of vital signs (including heart rate, breathing, blood pressure, body temperature and to measure blood pressure in a resting state);
2. Laboratory testing:
 - 1) Detection of anti-D immune response (using antibody screening test);
 - 2) Blood routine: including white blood cells (WBC), neutrophils (NEUT), hemoglobin (Hb), hematocrit (Hct), platelets (PLT);
3. Observation and recording of adverse events;
4. Combined treatment/medication.

(IV) Phase IV of Visiting: 1 month to 12 months after blood transfusion

1. Laboratory testing:
 - 1) Detection of anti-D immune response (using antibody screening test);
 - 2) "Asia type" DEL blood group typing.
2. Observation and recording of adverse events.

(V) Phase V of Visiting: Over 12 months after blood transfusion

1. Laboratory testing:
 - 1) Anti-D immune response test (using antibody screening test);
 - 2) "Asia type" DEL blood group typing.
2. Observation and recording of adverse events.

IX. Adverse events, serious adverse events

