In this trial, please report the serious adverse event report to the National Medical Products Administration, the National Health and Family Planning Commission in a timely manner according to the following contact information, and notify the research institution regularly.

The investigator must complete a Serious Adverse Event Report Form, and should record the time, the way, and to whom to report the serious adverse events in the original data. The sponsor guarantees it to satisfy all reporting requirements of laws and regulations.

The institute to report	Contact department /person	Telephone
National Medical Products Administration (NMPA)	Registration department	[name]/[name]
Institute of clinical blood transfusion, Guangzhou Blood Center	[name]	[name]

In case of any serious adverse event unrelated to the trial method, the researchers shall withdraw from the clinical trial when they think it is necessary or the subject or his legal guardian requests to withdraw from the trial, and the withdrawal case shall complete the last laboratory examination.

(V) Follow-up of the adverse events

All adverse events should be followed up to the normal or baseline level, or the investigator can reasonably explain the abnormality and think that no follow-up is necessary to ensure the safety of the subjects. According to the type and severity of the adverse reactions, the follow-up methods can be selected as inpatient, outpatient, home visiting, and telephone visiting and other ways.

X. Quality control of the clinical trial

(1) Quality control measures

Both the sponsor and the investigator should adopt Standard Operating Procedure (SOP) to ensure the quality control and the implementation of quality assurance system of the clinical research. All the observation results and findings in the clinical research should be verified to ensure the reliability of the data and the conclusions in the clinical research origin from the original data. Quality control must be adopted at every stage of data processing to ensure that all data are reliable and processed correctly.

(II) Training of researchers

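### Withdrawal from the whole trial after an unrelated serious adverse event is allowed with no provision to continue anti-D screening, so data on the study aim can be lost in a way linked to illness

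*Combined protocol and SAP*

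**What the plan says.** - **Withdrawal rule.** Section IX(IV)2, on handling serious adverse events, provides that after a "serious adverse event unrelated to the trial method, the researchers shall withdraw from the clinical trial when they think it is necessary". A request by the subject or the legal guardian has the same effect. The sentence ends by requiring that "the withdrawal case shall complete the last laboratory examination". It does not say which tests that examination contains, when it is done, or whether anti-D is among them.
- **Follow-up after withdrawal.** Section IX(IV)1 adds: "It should follow up the cases withdrawn due to adverse events and adverse reactions". The rest of that sentence concerns how the event continues and resolves. It does not mention antibody sampling.
- **Study aim.** Section III opens: "The aim of this study is to analyze whether anti-D alloimmunization will occur in" these patients after D+ transfusion. Anti-D incidence is also the first safety indicator in the Protocol Abstract and in sections VI(III) and VII(II).
- **Schedule.** Section VIII(II) is the "Blood transfusion treatment period (0~1 days"). Sections VIII(III) and VIII(IV) list "Detection of anti-D immune response (using antibody screening test") at 1 day to 1 month and at 1 to 12 months. Section VIII(V) lists "Anti-D immune response test (using antibody screening test") beyond 12 months. The flow chart in section XV agrees.
- **Analysis.** Section XII(I) puts every subject with at least one transfusion in the safety set. Section XII(II)2 calls for safety data to be summarised by stage. It has no paragraph on anti-D and no rule for a missing anti-D result.

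**The concern.** The withdrawal rule does not separate leaving treatment from leaving observation. Once a treatment period of 0 to 1 days is over, nothing of that transfusion remains to be stopped. What a later withdrawal ends is the antibody screening, and the event that prompts it has already been judged unrelated to the transfusion.

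Two things are at stake. First, the lost results would be tied to serious illness, so they cannot be assumed missing at random. Section IX(I) counts any hospitalisation or prolonged stay as serious. The population is patients anaemic enough to need transfusion, followed beyond 12 months, so admissions for the underlying disease could qualify. Second, a patient who leaves after an early negative screen may remain in the denominator with no further chance of becoming a case. That can only lower the observed incidence or leave it unchanged, and a low incidence is the finding that would support the new transfusion strategy.

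**Working it through.** The plan states no figure on this point, so there is none to reproduce. The check is mainly a reading, followed by an illustration.

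**1. What continues after withdrawal**

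| Item | Continues? | Source |
|---|---|---|
| Course and outcome of the event | Yes | IX(IV)1, IX(V) |
| One last laboratory examination | Yes, content and timing undefined | IX(IV)2 |
| Remaining Phase III to V anti-D screens | Not stated | VIII(III) to (V) describe the schedule only |
| Rule for missing anti-D | None | XII |

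The undefined examination can be read in two ways. It may be a test at the time of exit, which could fall early in follow-up. Or it may be the last scheduled laboratory visit, Phase V, whose only laboratory items are the anti-D test and DEL typing. On the second reading the endpoint is captured. The text does not choose between them.

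**2. Direction of the effect on incidence**

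Let N be the number transfused, x the observed anti-D conversions, L the patients lost after an early negative, and m the unseen later conversions among them (0 ≤ m ≤ L).

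- If the lost patients stay in the denominator as non-events, the report is x/N and the truth is (x + m)/N. The report is equal or too low.
- If they are removed, the report is x/(N − L). Its bias depends on whether the lost patients differ in risk, and the direction is unknown.

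The plan does not say which applies.

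**3. Illustration**

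Inputs: N and L/N are assumptions, because the protocol gives no target number, SAE rate or withdrawal rate. Zero anti-D results are assumed observed. With zero events in n informative patients, the exact two-sided 95% upper limit is 1 − 0.025^(1/n).

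| Assumed N | No loss | 10% lost | 25% lost |
|---|---|---|---|
| 20 | n = 20: 16.8% | n = 18: 18.5% | n = 15: 21.8% |
| 40 | n = 40: 8.8% | n = 36: 9.7% | n = 30: 11.6% |
| 100 | n = 100: 3.6% | n = 90: 4.0% | n = 75: 4.8% |

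For example, at N = 40 with 10% lost, n = 40 − 4 = 36 and 1 − 0.025^(1/36) = 9.7%.

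The precision lost is modest. The larger uncertainty is the unknown status of those who left. At N = 40 with 4 lost, a reported 0/40 is compatible with anything from 0/40 to 4/40 (10%). With 10 lost, the range extends to 10/40 (25%). For scale, section III cites 53/231 = 22.9% in true D-negative recipients of D+ blood. These are bounds, not forecasts.

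**The case against.** The strongest reply is that the endpoint need not be lost at all. The last laboratory examination may mean the Phase V visit, and screens done before withdrawal are not discarded by any stated rule. This stands in part. A reader might infer that the rule substitutes an early exit test taken before an antibody could appear. The documents give neither the timing of that examination nor any anti-D kinetics. What remains is that sites can read the sentence either way, and nothing requires the intervening screens.

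Second, a reader might infer that early negatives will be counted as non-responders. No section says so, and summarising by stage would fit reporting per visit. The claim is therefore limited to what the silence permits.

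Third, a reader might treat the exposure as one-off. Section XII(I) allows one or more transfusions, and section V(4) provides for units from different donors. The point holds for each treatment period of 0 to 1 days, not for a single exposure.

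Fourth, some of the loss cannot be avoided. Deaths and withdrawal of consent fall outside any remedy, so the point concerns discretionary withdrawals, whose number is unknown.

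Finally, dropout item 3 in section IV(IV) might seem to repeat the fault. It covers the case "if the subject has an adverse event that prevents him/her from completing the clinical trial", which describes inability to complete and does not instruct withdrawal. It needs no change on this account.

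**Conclusion.** The point holds in a limited form. As written, section IX(IV)2 permits discretionary withdrawal from the whole trial for an event unrelated to the transfusion, and no section keeps such a patient in anti-D screening. This opens an avoidable route to missing data on the stated aim, and the loss would be linked to serious illness.

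A reader might go further and conclude that the trial will lose its key endpoint in its sickest patients. The documents do not support that: they do not identify who would be withdrawn or how many, and they require some laboratory examination before exit.

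The size cannot be computed. Under an assumed N of 40 with no anti-D observed, 10% or 25% lost raises the exact upper limit from 8.8% to 9.7% or 11.6%. Any understatement of incidence depends on lost patients being kept as non-events, which the plan neither states nor rules out.

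**What to change.** Leave all treatment decisions as they are, and add to section IX(IV)2:

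1. Discretionary withdrawal after an SAE unrelated to the transfusion does not end the scheduled Phase III to V anti-D screens. These continue, through hospital return visits or home follow-up, unless the patient withdraws consent or dies.
2. The last laboratory examination includes a dated anti-D screen. Its result counts only for the phase in which it was taken and is not a completed result for a later phase.

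The cost is two sentences and some effort to reach these patients. No visit is added, and the only test that might fall outside the schedule is the exit screen. The Protocol Abstract already provides for hospital return or home follow-up at Phase IV, and section X(III) says the sponsor supplies the related laboratory tests free. This is a cheap improvement.
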